COVER PAGE

NCT06079853

Date of Protocol Approval: 10/18/2023

Study Title: The Use of Physiologic Measures and Sleep Health Promotion to Identify and Mitigate Predisposing Factors of Suicidal Ideation in Nurses

PI: [name], RN, ANP-BC, FAAN

PI Contact: [contact]

Sponsor: Columbia University School of Nursing

STUDY PROTOCOL

The purpose of this study is to generate longitudinal pilot data that investigates 1) which factors (stressful life events, psychiatric characteristics, and work environment characteristics) are associated with stress and subsequent suicidal ideation; and 2) to explore the preliminary impact of an existing evidence-based sleep intervention, *Somni*^{®14}, on stress, psychological health, and suicidal ideation in working nursing professionals. The specific aims are:

Aim 1. To investigate associations between sleep, stressful life events (life stressors, discrimination, lateral violence), psychiatric characteristics (psychiatric diagnosis, subjective mood), work environment characteristics (workload, shift type and duration, overtime, nurse work environment, and team relations) and stress (self-reported and heart rate variability) in working nursing professionals while controlling for standard covariates known to influence stress. *Hypothesis 1:* Suboptimal work environment characteristics are positively associated with self-report and physiologic indicators of stress [heart rate variability (HRV)]. *Hypothesis 2:* Poor sleep (duration and quality) will be positively associated with self-report and physiologic indicators of stress (HRV).

Aim 2. To determine if stress exposure (self-report and HRV) are associated with predisposing factors (sleep, stressful life events, additional psychiatric characteristics, and work environment characteristics), and to explore whether stress mediates the effect of predisposing factors on suicidal ideation in working nursing professionals. *Hypothesis:* Nurses with low HRV are at higher risk for suicidal behavior when exposed to poor sleep, the presence of psychiatric characteristics (e.g. Depression), stressful life events, or suboptimal work environment characteristics (e.g., poor team relations).

Exploratory Aim. To explore the preliminary impact of an existing sleep intervention (*Somni*[®]) on self-reported stress, HRV, sleep, and psychiatric health outcomes including depression, burnout, and suicidal ideation.

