STUDY DESIGN. This study is a prospective pragmatic pilot trial to generate data needed to inform a fully-powered longitudinal study consisting of nurses across a wider geographic region. There are 4 study components:

1. Electronic Quantitative Surveys (baseline, Week 4 & Week 8) will consist of demographic questions and validated measures for personal characteristics, sleep, stressful life events, psychiatric characteristics, work environment factors, and all psychological health outcomes. (**Table 1**). The surveys will be administered 3 times (baseline, week 4 and week 8) to generate pilot longitudinal data.

2. Psychological Assessment (baseline). To confirm a preexisting psychiatric diagnosis, a *Structured Clinical interview for DSM-5 Diagnosis* (Research version) (SCID-5-RV) will be administered in-person by a Psychiatric Mental Health Nurse Practitioner (PMHNP) at baseline. SCID-5-RV is a semi-structured interview guide for making major DSM-5 diagnoses such as mood disorders, psychotic symptoms, substance use, sleep, and trauma- or stressor-related disorders and takes approximately 45-60 minutes to administer. Studies suggest that prior history of mental illness, such as depression, has been linked to suicide.

3. Physiologic Biomarkers (Weeks 1-8). Heart rate and sleep (hours/day) will be collected using a wearable device, *Oura ring*[®], a piece of jewelry that can be custom fit to each participant. Heart rate variability (HRV), a highly sensitive physiologic metric for stress, is the constant variation in milliseconds between beats, and controlled by the autonomic nervous system. Low HRV is a strong indicator of physiologic stress (fight or flight response) and has been associated with increased risk for suicide attempt. Studies have demonstrated high validity in the assessment of HRV and sleep using the *Oura ring*[®]. The device will also collect activity levels (steps/day) and sleep cycles, known confounders for stress levels.

TABLE 1. Study Variables and Measures

Variable	Operational Definition	Measure
Demographics	Age, Sex, Gender, Race, Ethnicity, marital status, household income, parental status, smoking history, substance use; years of nursing experience	Validated single-items
Sleep	Sleep quality and duration	Pittsburgh Sleep Quality Index ⁴⁴ ($\alpha = .83$) Oura ring [®] Somni [®] 14
Stress	Self-reported stress Heart Rate Variability	Perceived Stress Scale ⁴⁵ ($\alpha = .76$) Oura ring [®]

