4. Sleep Intervention (Weeks 4-8) *Somni*[®] is an evidence-based personalized sleep intervention aimed at promoting optimal sleep health and has demonstrated effectiveness in shift workers outside the healthcare sector (e.g. Disney). *Somni*[®] consists of a sleep kit and a smart phone application. The sleep kit is box of items with demonstrated past evidence of improving sleep health: Blue light blocking glasses, white noise machine, lavender spray, ear plugs, light blocking eye mask, and herbal tea. Rather than dictate a “one size fits all” approach to optimize sleep health, there is current evidence that individualized sleep interventions are recommended to optimize sleep quality. *Somni*[®] permits individualized sleep quality promotion and participants are able to select their preferred use, timing, and duration of each of the box contents. The kit is accompanied by a *Somni*[®] smartphone app that prompts participants to input the use of each component in the kit and provide a subjective sleep quality rating each day. Drs. [name] and [name] have partnered with the developers of *Somni*[®] who will provide free sleep kits and app access to our study participants. The *Somni*[®] app is interoperable with the *Oura Ring*[®] and will automatically sync all physiologic and sleep data together in one location, fully accessible to the participants, and displayed in graphs in the *Somni*[®] app that are easy to read and interpret (e.g. total daily steps; daily sleep hours). *Somni*[®] will be implemented Weeks 4 through 8 to investigate its preliminary impact on stress and suicidal ideation by comparing survey and physiologic metrics from Weeks 1-4.

STATISTICAL ANALYSIS

First, we will calculate composite scores of individual measures (sleep, stressful life events, psychiatric characteristics, and work environment characteristics). Descriptive statistics will be calculated including means

and standard deviations (normally distributed values), median and interquartile range (non- normally distributed variables), or absolute and relative frequencies (categorical variables). Outliers and missing data will be assessed (outliers > 3 standard deviations from the mean will be removed). Significance level will be set at $\alpha = 0.05$.

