Aim 2. We will classify nurses into quartiles of high (top 25%), medium (middle 50%), and low (bottom 25%) HRV. We will use descriptive statistics to examine individual measures and composite scores of factors (sleep, stressful life events, psychiatric characteristics, work environment characteristics) and suicidal behavior [C-SSRS score]. To evaluate the change in suicidal ideation over time and the impact of each factor composite score, we will fit conditional latent growth curve models using 3 data points. The models will be expressed such that, given mean HRV and baseline composite scores for each factor category: $y_{it} = (\mu_a + \mu_\beta \lambda_t + \gamma_1 HCC_i + \gamma_2 WEC_i) + (\zeta_{ai} + \zeta_{\beta i} \lambda_t) + \varepsilon_{it}$ where y_{it} is the C-SSRS score for nurse i at time t , μ_a is the latent variable for the intercept value (baseline score), μ_β is the random latent variable for slope (growth over time) for nurse i multiplied by the vector of factor loadings specifying time, λ_{it} , ε_{it} is the time-specific residual for nurse i , ζ_{ai} and $\zeta_{\beta i} \lambda_t$ are random components of the latent intercept and slope variables, respectively. Sleep, stressful life events and psychiatric characteristics are fixed (time-invariant) predictors. The factor loadings for time on slope can be fixed to adjust for gaps in outcomes, which would allow for modeling more distant (e.g., 2025) data from baseline without increasing the number of timepoints included in the model. Further, we anticipate fluctuations in HRV over time. To accommodate the change in trend, we will explore both linear and quadratic growth functions. Baseline global sleep scores (PSQI), stressful life events, psychiatric and work environment characteristics will serve as predictors of suicidal ideation change over time. Individual nurse characteristics and psychiatric characteristic controls will be included as an interaction term to compare curves across nurses. To explore whether stress mediates the effect of predisposing factors on suicidal ideation, we will compare the models assessing the effect of predisposing factors on suicidal ideation with and without the mediator outlined by Barron and Kenny difference method which be used to gauge the size of the mediation effect.

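### Aim 2's printed growth equation has no factor-by-time term although the text says the factors predict change; mean HRV has no stated window, and the curve crosses the start of Somni without a period term

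*Combined protocol and SAP*

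**What the plan says.** - **Timing (Study Design, components 1, 3 and 4).** Surveys, including C-SSRS, are given at baseline, Week 4 and Week 8. The ring records heart rate and sleep over Weeks 1-8. Somni "will be implemented Weeks 4 through 8 to investigate its preliminary impact on stress and suicidal ideation". The plan describes this assessment as made "by comparing survey and physiologic metrics from Weeks 1-4". The developers will "provide free sleep kits and app access to our study participants". No comparison group is described.
- **Model (Statistical Analysis, Aim 2).** "we will fit conditional latent growth curve models using 3 data points", given mean HRV and baseline composite scores. Linear and quadratic growth will both be explored; the reason given is fluctuation in HRV, not the start of Somni.
- **Printed mean structure (Aim 2).** mu_a + mu_beta·lambda_t + gamma_1·HCC_i + gamma_2·WEC_i. Neither factor term is multiplied by lambda_t, and there is no Somni or period term. HCC is not defined.
- **Stated role of the factors (Aim 2).** "Baseline global sleep scores (PSQI), stressful life events, psychiatric and work environment characteristics will serve as predictors of suicidal ideation change over time". A separate sentence says that nurse characteristics and psychiatric controls will enter as an interaction.
- **HRV.** Aim 2 groups nurses by HRV and conditions on mean HRV. The Exploratory Aim looks for an effect of Somni "on self-reported stress, HRV, sleep, and psychiatric health outcomes including depression, burnout, and suicidal ideation".

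**The concern.** Aim 2 asks which predisposing factors go with suicidal ideation and its change, and the pilot is meant to inform a fully powered study. Three things could make its coefficients hard to use.

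(a) An equation with factors on level only cannot answer a question about change.

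(b) An HRV mean over all eight weeks would mix the risk marker with any response to the intervention.

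(c) The Week 8 score is taken under Somni, which the protocol studies because it may alter suicidal ideation. If the fitted slope is carried forward as the factor's relation to natural change, a Somni effect that varies with the factor could create an apparent association or hide a real one. Variation between nurses is plausible because participants choose how, when and for how long to use each item, but the documents give no size for it.

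**Working it through.** The documents state no sample size, SD or effect size, so there is no planned figure to reproduce. Notation: time t = 0, 1, 2 in 4-week intervals; sigma = residual SD; tau² = random-slope variance in sigma²; factor in SD units; d = Somni's mean effect on C-SSRS at Week 8; d1 = its difference per unit of the factor. Values of n, tau² and d1 below are assumptions.

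**(a) Equation against text.** With gamma·F_i on level only, the expected change between any two visits is mu_beta times the difference in lambda_t. This is the same for every value of F, so no parameter carries a factor's effect on change. The interaction sentence could supply one for nurse characteristics and psychiatric controls, but it does not name sleep, life events or work environment. Fitted literally, a true factor-to-slope effect leaks into gamma. The share is not fixed: at tau² = 0.25 and intercept variance 1 (sigma²), it is 1.00, 0.67 and 0.33 for intercept-slope correlation -0.5, 0 and +0.5.

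**(b) HRV window.** If Weeks 5-8 are the Somni weeks, they are half of the eight ring weeks, so the 8-week mean equals the pre-Somni mean plus half of the nurse's HRV response. A uniform response changes no one's HRV group. If the response varies independently of pre-Somni HRV with SD 0.25, 0.5 or 1.0 of the between-nurse SD (assumed), simulation gives about 6%, 12% or 23% of nurses in a different group.

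**(c) Slope across the start of Somni.**
- With equal residual variances, the linear slope weights on the three visits are (-1/2, 0, +1/2), whatever the random-effect variances.
- A Week 8 effect of d + d1·F therefore moves the mean slope by d/2 and the factor-to-slope coefficient by d1/2 per interval, which is d1/8 per week.
- If the Week 8 residual variance is double, the weights are (-0.571, 0.143, 0.429) and the shift is 0.43 d1. If it is half, they are (-0.455, -0.091, 0.545) and the shift is 0.55 d1.
- If d1 = 0, the factor coefficient does not shift; only the mean slope does.

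*Illustration.* True factor-to-slope effect 0, two-sided 5% test, noncentral t with n - 2 degrees of freedom, standard error sqrt((tau² + 0.5)/n), tau² = 0.25:

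| d1 (sigma) | n = 25 | n = 50 |
|---|---|---|
| 0.2 | 9% | 13% |
| 0.4 | 20% | 36% |
| 0.6 | 38% | 67% |

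At tau² = 1 and n = 50, the rates at d1 = 0.4 and 0.6 are 21% and 40%. In the other direction, with a true effect of 0.30 sigma, n = 50 and tau² = 0.25, power falls from 67% at d1 = 0 to 13% at d1 = -0.4. These figures treat C-SSRS residuals as approximately normal.

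**What three visits can separate.** In the quadratic form with factors on both growth terms, the linear plus quadratic coefficient has weights (-1, 1, 0). It is exactly the baseline-to-Week 4 factor contrast. The terms 1, t, t² and a Week 8 step have rank 3, so a Somni effect and natural curvature cannot be told apart. The Week 8-by-factor term has weights (1, -2, 1) and per-nurse variance 1 + 4 + 1 = 6 sigma². At n = 50 its power is about 20% at d1 = 0.4 and 40% at d1 = 0.6.

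**The case against.** **The target may be change as observed.** Aim 2 speaks of change in suicidal ideation over time and nowhere calls the slope change without Somni. How factors relate to change in the study as run, Somni included, is a coherent target, and for that target d1 is part of the answer. This stands. A reader might infer that the Aim 2 estimates are biased as planned; the documents do not support that, because the shift needs both the natural-course reading and a non-zero d1.

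**The quadratic form already holds the contrast.** This is true if factors load on both growth terms, but the plan does not say that they will and does not name the contrast. The remedy is therefore mainly labelling.

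**Aim 3 covers Somni.** Its separate models use each nurse's mean kit-use frequency. That is not a period term and adds nothing to the Aim 2 curve.

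**The equation may be shorthand.** A reader might infer that no factor-by-time term will be fitted. The text says the factors predict change, so the supportable claim is a mismatch that leaves the printed model unable to answer the stated question.

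**Week 4 is probably pre-Somni.** Using Weeks 1-4 as the comparison period suggests so, and a reader should not conclude that the Week 4 survey is contaminated. But Week 4 lies in both periods as worded, so the order is not settled.

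**The scenarios are chosen.** They are. No n, sigma or d1 comes from the documents, and the rates vary widely across the range shown.

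**Conclusion.** The Aim 2 equation is wrong as written: it has no coefficient for the factor-to-change question that the text poses. This needs no assumption about Somni.

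The rest is a cheap improvement. The HRV window is unstated, and an 8-week mean would mix marker and response by an unknown amount. The absence of a period term matters only if the linear slope is read as change without Somni and Somni's effect differs by factor. The shift is then about d1/2 per 4-week interval, in either direction, and zero if d1 = 0. The rejection and power figures illustrate sensitivity and do not predict this trial's error rates. Confidence is medium, because the size of d1 and the intended reading of the slope are both unknown.

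**What to change.** 1. Correct the equation so that each factor also multiplies lambda_t, and define HCC.
2. State that mean HRV for Aim 2, both for grouping and for conditioning, comes from the pre-Somni weeks only.
3. Keep the 3-visit linear model, and do not describe its slope as change without Somni. Beside it, report the baseline-to-Week 4 factor contrast as a prespecified sensitivity analysis; in the planned quadratic form with factors on both growth terms, it is the linear plus quadratic coefficient. State that three visits cannot separate Somni from natural curvature, and that a null Week 8-by-factor term is weak reassurance.
4. Reconcile Weeks 1-4 with Weeks 4 through 8 so that it is clear whether the Week 4 survey precedes Somni. If Week 4 already carries a share p of the effect, the contrast shifts by p·d1, which is smaller than d1/2 only when p < 0.5.

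**Cost.** SAP wording and one extra model; no new data. Factor intervals in the sensitivity analysis are wider by sqrt((tau² + 2)/(tau² + 0.5)): 2.0, 1.73, 1.41 and 1.26 times at tau² = 0, 0.25, 1 and 2. With Week 4 unexposed, the contrast has the lower mean squared error only when d1²/4 exceeds 1.5 sigma²/n, that is |d1| > 2.45 sigma/sqrt(n) (0.49 sigma at n = 25, 0.35 sigma at n = 50). It therefore belongs beside the linear model and should not replace it. Fewer HRV nights cost little: by k·ICC/(1 + (k - 1)·ICC), with an assumed nightly intraclass correlation of 0.4 to 0.8 and independent night-to-night error, reliability is 0.949 to 0.991 on 28 nights against 0.974 to 0.996 on 56.

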Aim 1. We will calculate bivariate Pearson or Spearman's rank order correlation coefficients as well as simple linear regression and univariate ANOVAs. We will use linear mixed models to examine the relationships between individual and composite scores of factors (sleep, stressful life events; psychiatric characteristics; work environment characteristics) and 1) self-report stress and 2) HRV, while controlling for personal characteristics (age, sex, highest degree earned, years of experience, years of practice in current environment, smoking status). We propose the following model to test all hypotheses:

$Y_g[E(i)] = \beta_0 + \beta_1 X_i + \beta_2 F$ where Y_g represents the outcomes measure (self-report and HRV separately) for each participant i . X_i are the individual-level covariates (e.g., sex, gender, race, age, mental health history), F represents each job stressor and work environment variable. As the primary outcome is stress (mean score and mean HRV), possible distributions such as Poisson, zero-truncated Poisson, negative binomial, or zero-truncated negative binomial will be assessed to determine the best fit link function.

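### The 3-SD outlier rule has no exemption for C-SSRS and could delete the highest ideation scores; separately, no distribution check or robust interval is planned for a C-SSRS score that may be mostly zero.

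*Combined protocol and SAP*

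**What the plan says.** All references are to the Combined protocol and SAP.

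- **Statistical Analysis, opening paragraph.** After composite scores and descriptive statistics, the plan states that "outliers > 3 standard deviations from the mean will be removed". No variable is exempted. The text does not say whether the rule is applied once or repeatedly, or by wave or pooled.
- **Aim 1.** The distribution check follows the words "As the primary outcome is stress (mean score and mean HRV". It reads "possible distributions such as Poisson, zero-truncated Poisson, negative binomial, or zero-truncated negative binomial will be assessed to determine the best fit link function".
- **Aim 2.** For suicidal ideation "we will fit conditional latent growth curve models using 3 data points". The modelled quantity "is the C-SSRS score for nurse i at time t", and the error term "is the time-specific residual for nurse i". The equation adds intercept, slope, predictors, random components and residual. It names no link, residual distribution or estimator. The plan adds that "we will explore both linear and quadratic growth functions".
- **Aim 3.** Mean C-SSRS is again a dependent variable and growth curves are again fitted, with no distribution named.

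The documents do not state how C-SSRS is scored, its range, the expected share of nurses at zero, or the sample size.

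**The concern.** Two separate issues arise if C-SSRS is zero for most nurses.

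First, with many zeros both the mean and the SD are small, so mean plus 3 SD falls inside the range of genuine ideation scores. A rule meant to catch aberrant values then removes the most severe true values of the Aim 2 outcome.

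Second, the variance of such a score rises with its mean. A predictor that shifts the mean therefore also shifts the variance, and a standard error that assumes constant variance can be wrong for the predictors of most interest. The plan looks for a suitable distribution for stress and is silent on C-SSRS. Results from this pilot are meant to inform a larger study, so trimmed ideation scores and understated uncertainty would carry forward into its design.

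**Working it through.** The plan gives no figure to reproduce. Everything below rests on assumptions, which are stated.

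**1. The 3-SD rule, uniform scores.** Assume a proportion p of nurses is non-zero, with scores uniform on 1 to 5. Among the non-zero, the mean is 3 and the mean square is (1+4+9+16+25)/5 = 11. Overall, mean = 3p, variance = 11p − 9p², and cut = 3p + 3·SD, applied once.

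| p | Mean | Variance | SD | Cut | Scores removed | Share of non-zero |
|---|---|---|---|---|---|---|
| 0.05 | 0.15 | 0.5275 | 0.73 | 2.33 | 3, 4, 5 | 60% |
| 0.10 | 0.30 | 1.01 | 1.00 | 3.31 | 4, 5 | 40% |
| 0.20 | 0.60 | 1.84 | 1.36 | 4.67 | 5 | 20% |
| 0.40 | 1.20 | 2.96 | 1.72 | 6.36 | none | 0% |

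**2. The 3-SD rule, latent-normal scores.** Assume instead an ordinal 0 to 5 score cut from a latent normal.

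| Zeros | Mean | SD | Cut | Share of non-zero removed |
|---|---|---|---|---|
| 60% | 1.008 | 1.526 | 5.59 | 0% |
| 80% | 0.426 | 1.024 | 3.50 | about 16% |
| 85% | 0.304 | 0.863 | 2.89 | about 28% |
| 90% | 0.190 | 0.674 | 2.21 | about 24% |
| 95% | 0.088 | 0.447 | 1.43 | about 46% |

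The amount depends on the score model. In both models the values removed are the top of the scale.

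**3. Interval width, two-group contrast at one wave.** Use the uniform model, with 20% ideators in group A (variance 1.84) and 5% in group B (variance 0.5275); the variance ratio is 3.5. For shares a and 1 − a:

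- true SE² ∝ 1.84/a + 0.5275/(1 − a)
- constant-variance SE² ∝ [1.84a + 0.5275(1 − a)]·[1/a + 1/(1 − a)]
- coverage = 2Φ(1.96/R) − 1, where R is true SE over constant-variance SE

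At a = 0.25 these are 8.063 and 4.563, so R = 1.33 and coverage is 0.86. At a = 0.50 both are 4.735, so R = 1.00 and coverage is 0.95. At a = 0.75 they are 4.563 and 8.063, so R = 0.75 and coverage is 0.99.

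At a = 0.25, 20% versus 10% gives R = 1.16 and coverage 0.91; 30% versus 5% gives R = 1.40 and coverage 0.84. With the split reversed, coverage over the three contrasts is 0.98 to 0.99. The direction of the error therefore depends on which group is larger.

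**4. Interval width, three waves.** This simulation used the latent-normal 0 to 5 score, complete data, N = 50, 100 and 200, and 3,000 runs per setting. The predictor was binary (20%) or continuous, with no effect or a latent effect of 0.8 SD, with or without a change over time. Least squares on each nurse's mean and slope gave the level and slope effects. Coverage of nominal 95% constant-variance intervals was:

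- unrelated predictor: about 0.92 to 0.96 at every share of zeros;
- related predictor, 30% zeros: 0.94 to 0.99;
- related predictor, 60% zeros: 0.88 to 0.92 (binary), 0.93 to 0.97 (continuous);
- related predictor, 80% zeros: 0.80 to 0.92;
- related predictor, 90% zeros: 0.73 to 0.87 (0.77 to 0.87 at N = 200);
- related predictor, 95% zeros: 0.66 to 0.81.

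**5. Robust (HC2) intervals on the same data.** For a related predictor, coverage was 0.87 to 0.95 at 80% zeros, 0.79 to 0.96 at 90% and 0.72 to 0.96 at 95%. At N = 200 the ranges were about 0.93 to 0.95, 0.90 to 0.95 and 0.87 to 0.96. For an unrelated binary predictor's level effect, coverage fell to about 0.85 to 0.93 at 80% to 95% zeros. An ordinal model was not fitted in this check.

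**The case against.** The strongest objection is that the zero share is not in the documents. Nothing gives C-SSRS scoring, prevalence or sample size, and the planned diagnostic interview to confirm existing psychiatric diagnoses means a low-ideation sample cannot be taken for granted. This stands, and every figure here is conditional on it.

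A reader might infer that the ideation intervals will be wrong whenever most nurses score zero. The documents do not support that. Aim 2 enters mean HRV and composite scores, not a 25/75 group contrast, and undercoverage in the two-group calculation vanishes at an even split and reverses beyond it. In a one-wave check with a continuous predictor and 20% non-zero scores, coverage was about 0.95 at an odds ratio of 1.5 per SD and 0.92 to 0.94 at 3. The lower three-wave figures use a large effect.

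A reader might also infer that count models are ruled out for C-SSRS, or that constant-variance normal errors are specified. The plan is silent on both; constant variance is the default reading of an additive equation, not a stated choice. The quadratic growth option changes the time shape and does not address the error distribution.

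Finally, this is a pilot with stress as its primary outcome, and the mediation question is exploratory. That limits the priority of the modelling issue. It does not excuse the outlier rule, whose correction costs almost nothing.

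**Conclusion.** The point holds in two parts, of unequal strength.

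- **Outlier rule (firmer).** As written it covers C-SSRS. If about 80% or more of scores are zero, it removes genuine high ideation scores: 20% to 60% of non-zero scores at 20% to 5% prevalence under uniform scores, about 16% to 46% over 80% to 95% zeros under the latent-normal model. At 60% zeros it removes none under either model.
- **Interval width (conditional).** The plan has no link, distribution check or robust estimator for C-SSRS. If the score is zero-heavy, model-based intervals for predictors truly related to ideation can have the wrong width, often too narrow from about 80% zeros, and a sample of 200 did not cure this. Intervals for unrelated predictors stay near 95%, as do those for continuous composites at about 60% zeros.

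Both parts rest on an assumed 0 to 5 score and an assumed zero share; the second also rests on the assumed effect size, sample size and constant-variance estimation.

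**What to change.** 1. State how C-SSRS is scored. Exempt it from the 3-SD removal and check high values only for data-entry error. This is one sentence and needs no new data.
2. Extend the distribution check to C-SSRS, with options that allow excess zeros. Copying the Aim 1 list would not be enough: its zero-truncated forms cannot produce a zero, and it names no zero-inflated, hurdle or ordinal model.
3. When there are enough ideators, use an ordinal (cumulative-logit) growth model with a nurse random intercept, one composite at a time. State in advance how many ideators count as enough.
4. Otherwise keep the linear growth curve, report bootstrap or nurse-clustered robust intervals, and give the any-ideation analysis as a sensitivity analysis. It should not replace the main analysis, because it discards severity.
5. Apply the same wording to the C-SSRS models in Aim 3.

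The cost is plan wording and a different model in the analysis. The downsides are odds ratios in place of mean differences, few predictors per model, and robust intervals that only partly restore coverage in small samples. With an assumed N = 50 and 5% prevalence, 50 × 0.05 = 2.5 ideators, so the ordinal or logit model may not be estimable; step 4 is there for that case.
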